5.6. Visit Windows

For tabular and graphical summaries, all data will be tabulated and analyzed per the evaluation visit as recorded on the electronic case report forms (eCRF) even if the assessment is outside of window.

Unless otherwise specified, data collected at an unscheduled visit will be included in by-patient listings and/or spaghetti plot figures, but no assignment of the scheduled visit will be made for the purposes of summary tabulations. However, unscheduled study visits will be used in the calculation of baseline values if prior to first dosing and for any categorical shift tables (eg shift from baseline to worst post-baseline value).

The following are time windows for the analysis of Plasma Oxalate Profile samples in Cohort B:

Blood Collection Sampling time	Window
Pre-Dialysis	Prior to dialysis on the same day as the dialysis
30 minutes before end of dialysis	from 1 hour prior to end of dialysis through the end of dialysis
30 minutes post-dialysis	after the end of dialysis through 1 hour post-dialysis
2 hours post-dialysis	>1 hour post-dialysis through 3 hours post-dialysis
4 hours post-dialysis	>3 hours post-dialysis through 6 hours post dialysis
8 hours post-dialysis	>6 hours post-dialysis through 10 hours post-dialysis
12 hours post-dialysis	>10 hours post-dialysis through 16 hours post-dialysis
24 hours post-dialysis	>18 hours post-dialysis through pre-dialysis the next day (if dialysis session scheduled day after current dialysis) or 29 hours post-dialysis (if no dialysis session scheduled day after current dialysis)

5.7. Interim Analysis

Potential interim database extractions may be planned for lumasiran regulatory submission purposes and/or publication requests.

5.8. Analysis for Primary Endpoint and Database lock

As this study will be ongoing at the time of the primary analysis, the study database will have a Primary Analysis Period database lock when the last patient completes all Month 6 visit assessments. All data entered as of the date of the Primary Analysis Period database lock will be included in the summary of the Primary Analysis Period CSR.

After the study is completed (ie all patients complete the Long-term Extension Period and/or required safety follow-up visit(s)), the final database lock will occur, and all data will be summarized in a final CSR.

6. STUDY ANALYSES

6.1. Patient Disposition

Number and percentage of patients will be tabulated by Cohort for the following categories:

- Safety Analysis Set
- Full Analysis Set
- PK Analysis Set

Summaries of the number and percentage of patients who discontinued treatment and/or withdrew from the study will be presented, along with the primary reasons for discontinuation of treatment and/or withdrawal from the study. Additionally, the number of patients who completed the Month 6 visit will also be displayed. A patient is defined as having completed the Month 6 visit if the patient has at least one blood sample for plasma oxalate (Cohort A) or pre-dialysis plasma oxalate (Cohort B) for the Month 6 visit.

An individual patient is considered to have reached the end of the study if:

- the patient has completed the end of study (EOS; Month 60) visit, or
- the patient has completed 12 months of monitoring following the final lumasiran dose.

The number and percentage of patients enrolled by country and site will be summarized.

Data listings of those patients who withdrew and/or discontinued treatment including the associated reasons will also be presented. Disposition will be summarized throughout the study. All disposition analyses will be presented by cohort.

6.2. Demographics and Baseline Characteristics

Descriptive statistics of demographic characteristics including but not limited to: age, weight (kg), weight category (0-<10kg, 10-<20kg, \geq 20kg), gender, race, ethnicity, region, height (cm), and body mass index (BMI) will be presented. The modified Z-score for patients under age 18 will be calculated and summarized for height, weight and body mass index (BMI) according to the Centers for Disease Control and Prevention (CDC) growth chart.[CDC National Center for Health Statistics 2019]

Additional disease characteristics will be summarized using descriptive statistics. These include but are not limited to: spot urinary oxalate:creatinine ratio (mmol/mmol), plasma oxalate (umol/L), plasma oxalate AUC [umol/L/24hr] (Cohort B only), 24-hour urinary oxalate excretion corrected for BSA (mmol/24hours/1.73m²), 24-hour urinary oxalate:creatinine ratio (mmol/mmol), eGFR (Cohort A only), spot and 24 hr. urinary glycolate:creatinine ratio (mmol/mmol), plasma glycolate (nmol/L), number of episodes with renal stone events, number of patients reporting pyridoxine (vitamin B6) use at the time of study entry, and presence of systemic oxalosis (Cohort B).

All analyses will be presented by Cohort.

6.3. Medical History

A complete medical and surgical history will be collected at the screening visit. The medical and surgical history will be coded using the Medical Dictionary for Regulatory Activities (MedDRA Version 21.1 or later) and will be summarized for the Safety Analysis Sets.

A tabular summary of historical disease characteristic information will be generated and include information on disease characteristics such as: time from diagnosis to first dose date (months), time from first symptoms to first dose date (months), time from first symptoms to diagnosis (months), number of siblings with PH1, reported history of disease events (eg pyelonephritis, renal stones, kidney stones, urinary tract infection). Reported medical history events may be adjusted based on age category, see Section 10.1.

Separate by-patient listings will be generated.

6.4. Prior and Concomitant Medications

Prior and concomitant medications will be coded using the World Health Organization (WHO) Drug Dictionary (September 2018 or later). Prior medications are defined as medications that were taken prior to and were either ongoing at the time of or stopped before the first dose of the study medication. Concomitant medications are defined as medications which were taken prior to and were ongoing while on lumasiran or medication(s) taken on or after the first dose date of the lumasiran.

A tabular summary of the number and percentage of subjects taking concomitant medications will be generated by anatomic therapeutic class (ATC) and preferred term. Data will be presented for the Safety Analysis Set.

By-patient listings will be generated separately for prior medications, concomitant medications and pyridoxine (vitamin B6). By-patient listings for crystallization inhibitors and erythropoietin (EPO) stimulating agents may also be provided.

7. STATISTICAL ANALYSIS

All endpoints in ALN-GO1-005 will be analyzed by Cohort.

7.1. Primary Endpoint

The primary objective in Cohort A is to evaluate the effect of lumasiran on plasma oxalate in patients who are not on dialysis therapy. The primary objective in Cohort B is to evaluate the effect of lumasiran on pre-dialysis plasma oxalate levels in patients who are on hemodialysis therapy. The primary endpoint is percent change from baseline in plasma oxalate (Cohort A) / pre-dialysis plasma oxalate (Cohort B) to Month 6.

The primary analysis in Cohort A will be performed using a restricted maximum likelihood (REML) based Mixed-effect Model Repeated Measures (MMRM) approach using the FAS. Analysis will include evaluable plasma oxalate values of all scheduled visits through Month 6, which will be modeled with fixed effects of scheduled visits and baseline plasma oxalate, including patient as a random factor. Autoregressive (1) will be used to model the within-patient error given the small sample size for this study. The primary estimate is the least square (LS) mean of the percent change in plasma oxalate from baseline at Month 3 to Month 6, averaged over these timepoints. This LS mean will be presented along with corresponding standard errors (SEMs), 95% confidence intervals (CI) and p-value from the model (ie, testing against the null hypothesis of mean of primary outcome being equal to 0).

If the fit of the autoregressive (1) covariance structure matrix fails to converge, the primary estimate is the LS mean of the primary outcome variable average across scheduled visits from Month 3 to Month 6, according to analysis of covariance (ANCOVA) model with covariate of baseline plasma oxalate. This LS mean will be presented along with corresponding SEMs, 95% CI and p-value from the model.

The primary analysis in Cohort B will be performed using a REML based MMRM approach using FAS. Analysis will include evaluable pre-dialysis plasma oxalate values of all scheduled visits through Month 6, which will be modeled with fixed effects of scheduled visits and pre-dialysis baseline plasma oxalate, including patient as a random factor. Autoregressive (1) will be used to model the within-patient error given the small sample size for this study. The primary estimate is the LS mean of the percent change in plasma oxalate from baseline at Month 3 to Month 6, averaged over these timepoints. This LS mean will be presented along with corresponding standard errors (SEMs), 95% confidence intervals (CI) and p-value from the model (ie, testing against the null hypothesis of mean of primary outcome being equal to 0).

If the fit of the autoregressive (1) covariance structure matrix fails to converge, the primary estimate is the LS mean of the primary outcome variable average across scheduled visits from Month 3 to Month 6, according to the ANCOVA model with covariate of pre-dialysis baseline plasma oxalate. This LS mean will be presented along with corresponding SEMs, 95% CI and p-value from the model.

For each cohort, descriptive statistics and LS mean will also be generated at each scheduled visit. Mean (+/- SEM) figures of percent reduction will be plotted as well as individual spaghetti plots. A table of the mean maximum percent reduction during the 6-months will also be generated. The forgoing analyses will be performed using data from Primary Analysis Period of each cohort.

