1.2.2. Summary of Clinical Data with Lumasiran

Lumasiran is being investigated in 4 clinical studies, 3 of which are currently ongoing. Study ALN-GO1-001 is a Phase 1/2 study, and was completed in 2 parts (single-ascending dose [SAD; Part A] and multiple-ascending dose [MAD; Part B]), in healthy adult subjects and adult and pediatric patients (≥ 6 years old) with PH1. In this study, healthy adult subjects in Part A were randomized to receive a single-blind dose of lumasiran (0.3-6.0 mg/kg) or placebo (6:2). In Part B, patients ≥ 6 years of age with PH1 and preserved renal function (eGFR >45 mL/min/1.73 m 2) were randomized 3:1 to receive single-blind doses of lumasiran or placebo at 1.0 mg/kg monthly for 3 doses, 3.0 mg/kg monthly for 3 doses, or 3.0 mg/kg every-3-months for 2 doses. Patients in Part B on placebo transitioned to the open-label portion of the study to receive lumasiran.

Available preliminary data from Study ALN-GO1-001 demonstrate a mean maximal reduction in 24-hour urinary oxalate of 64% (Cohorts 1 to 3) and achievement of normal to near-normal levels of urinary oxalate (<0.7 mmol/24h/1.73 m 2) in patients dosed with lumasiran (range: 0.29 to 0.67 mmol/24h/1.73 m 2). This suppression of urinary oxalate was maintained with repeat dosing, indicative of the durability of the pharmacodynamic effect of lumasiran. In addition, in the multiple-ascending dose group (Part B; n=10), preliminary data showed a mean reduction of 59% in plasma oxalate relative to baseline 28 days after the last dose. The mean maximal reduction in plasma oxalate was 75% (range 57-94%), and 50% of patients achieved plasma oxalate levels within the normal range (<1.6 μ mol/L).

Study ALN-GO1-002 is an ongoing Phase 2 open-label extension study to evaluate the long-term safety, PK, and PD of lumasiran in patients with PH1 who completed Study ALN-GO1-001.

In the ALN-GO1-001 and ALN-GO1-002 clinical studies, available data indicate that lumasiran has an acceptable safety and tolerability profile across all dosing regimens with no drug-related serious adverse events (SAEs) or study discontinuations attributed to drug administration.

Additional detailed information on the chemistry, pharmacology, efficacy, and safety of lumasiran is provided in the Investigator's Brochure.

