2. STUDY OVERVIEW

2.1. Synopsis of Study Design

The ILLUMINATE-C study (ALN-GO1-005) is a multicenter, multinational, open-label, single arm Phase 3 study designed to evaluate the efficacy, safety, PK and PD of lumasiran in patients with a documented diagnosis of PH1 who have advanced renal disease, as evident by eGFR ≤ 45 ml/min/1.73 m² (or serum creatinine elevated for age, in patients <12 months of age). All eligible patients will be administered open-label lumasiran; no control group will be assessed. This study will consist of 2 periods: a 6-month Primary Analysis Period followed by a long-term (54 months) extension period.

Lumasiran will be administered as a subcutaneous (SC) injection with weight-based dosing, with dose adjustments for interval weight gain, as follows:

Weight	Loading Dose (Day 1, Month 1, Month 2)	Maintenance Dose (Month 3 and Beyond)
<10 kg	6.0 mg/kg monthly for 3 months	3.0 mg/kg monthly
≥ 10 to <20 kg	6.0 mg/kg monthly for 3 months	6.0 mg/kg every 3 months
≥ 20 kg	3.0 mg/kg monthly for 3 months	3.0 mg/kg every 3 months

For patients <6 years of age, the dose will be based on a weight obtained within 7 days prior to dosing. In patients ≥ 6 years of age, body weight collected within 3 months prior to the study drug dose or the predose weight collected on the study visit day or dosing day will be used for dose calculations.

Patients with weight increases crossing the threshold for the next weight-based dosing category (for example, <10 kg to ≥ 10 kg or <20 kg to ≥ 20 kg) will follow the new dosing regimen for the remainder of the study or until the next dosing category threshold is reached (ie, patients will not switch back to the lower-weight dosing schedule if their body weight subsequently decreases).

Patients in maintenance dosing who transition from <10 kg to ≥ 10 kg will continue to receive monthly doses at 3.0 mg/kg until the next quarterly visit (ie Month 3, Month 6, Month 9, etc.) whereby they will follow every 3-months dosing until the end of the study.

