AUC(0-24h) will be calculated using plasma oxalate results with the linear-trapezoidal method using actual collection times relative to pre-dialysis sampling time. An exact 24h assessment for the purpose of calculating the AUC(0-24h) will be calculated using linear interpolation or extrapolation on the two non-missing scheduled assessments closest to the 24-hour timepoint.

Plasma oxalate profiles will be compared across visits within patients. LS mean percent change from baseline plasma oxalate AUC(0-24h) at Month 6 and its associated 95% confidence interval will be estimated using MMRM model including data evaluated at Month 3 and Month 6. Additionally, the AUC(0-24h) parameter will be listed and descriptively summarized by study visit. The Full Analysis Set will be used for this analysis. A similar approach as used for the primary analysis will apply, in case when the model fails to converge.

Additionally, AUC(4-24h) will be similarly analyzed. AUC(4-24h) is defined as the plasma oxalate area under the curve of the 20 hour window from the end of dialysis (30 minutes before the end of dialysis assessment) until the next dialysis session (24h timepoint). This approach is intended to reduce the variability introduced by different dialysis parameters between patients. The percent change from baseline in plasma oxalate AUC(4-24h) will be summarized through Month 6 in a similar manner to the percent change from baseline in plasma oxalate AUC(0-24h) as a sensitivity analysis to the secondary endpoint. The pre-dialysis scheduled assessment will not be required for a valid AUC or utilized in this assessment, otherwise this analysis will remain consistent with methodology to assess the percent change from baseline in plasma oxalate AUC(0-24h).

7.3.2. Change from baseline to Month 6 in other Plasma and Urinary Oxalate Parameters

The analyses for the following secondary endpoints will also be performed using a restricted maximum likelihood based Mixed-effect Model Repeated Measures approach.

- Absolute change from baseline to Month 6 in plasma oxalate during the Primary Analysis Period
- Percent change and absolute change from baseline to Month 6 in 24-hr urinary oxalate corrected for BSA during the Primary Analysis Period
- Percent change and absolute change in spot urinary oxalate: creatinine ratio during the Primary Analysis Period

[figure not shown]

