Analysis by cohort will include evaluable assessments through Month 6, which will be modeled with fixed effects of scheduled visits and baseline covariate of corresponding assessment,

including patient as a random factor. LS mean of an endpoint of Month 3 to Month 6, averaged over these timepoints will be presented along with corresponding SEMs and 95% CIs. The autoregressive (1) covariance structure matrix will be used to model the within-patient error given the small sample size for this study. Similar approach as used for the primary analysis will apply, in case when the model fails to converge.

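### Baseline as a covariate in a single-arm model leaves the mean oxalate change unaltered but understates its standard error to the extent that baseline explains the outcome

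*SAP*

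**What the plan says.** The study is single-arm: "All eligible patients will be administered open-label lumasiran; no control group will be assessed" (SAP 2.1).

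For Cohort A, SAP 7.1 fits a REML repeated-measures model to plasma oxalate at scheduled visits through Month 6, "which will be modeled with fixed effects of scheduled visits and baseline plasma oxalate, including patient as a random factor", with AR(1) within-patient errors. Cohort B has the same structure: "which will be modeled with fixed effects of scheduled visits and pre-dialysis baseline plasma oxalate, including patient as a random factor". The primary estimate is the LS mean percent change averaged over Months 3 to 6. Its SE, CI and p-value come from the model, the p-value "testing against the null hypothesis of mean of primary outcome being equal to 0". If the AR(1) fit does not converge, the Month 3-6 average is analysed "according to analysis of covariance (ANCOVA) model with covariate of baseline plasma oxalate", and the Cohort B fallback uses pre-dialysis baseline in the same way.

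SAP 7.3.2 carries the rule to other endpoints, "modeled with fixed effects of scheduled visits and baseline covariate of corresponding assessment", reporting LS means, SEs and 95% CIs. Its list includes "Absolute change from baseline to Month 6 in plasma oxalate during the Primary Analysis Period".

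Neither section names a degrees-of-freedom method, says that inference is conditional on the observed baselines, or adds back the variance that baseline explains.

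**The concern.** Between randomised arms, adjusting for baseline sharpens a difference. Here there is one arm and one mean. The LS mean is evaluated at the sample's average baseline, and with complete data it is the raw mean. The covariate therefore does not improve the estimate; it only lowers the residual variance from which the SE is built. The mean change in the population also varies with which baselines happen to be enrolled, and that part is left out.

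At stake are the error bars on the primary result in each cohort and on absolute change in plasma oxalate. Enrolling more patients does not cure the shortfall, because the SE is short by the same proportion at any n.

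**Working it through.** **Inputs.** Two-sided 95% CIs (SAP 5.2). Twenty patients with at least 6 per cohort (SAP 5.1), so 6 to 14 in a cohort. The sample size rests on feasibility, so the plan gives no SD, SE or CI width to reproduce. R2, the share of the variance of a patient's Month 3-6 average that baseline explains, is also not given and is varied below.

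**Algebra (complete data).** Centred baseline is orthogonal to the visit terms, so the LS mean equals the raw mean.
- Model variance: residual variance / n.
- Variance of the unconditional mean: (residual variance + slope^2 x var(baseline)) / n.
- SE ratio: sqrt(1-R2), which is 0.95, 0.87 and 0.71 at R2 = 0.1, 0.25 and 0.5.

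**Primary endpoint, ANCOVA fallback (exact under normality).** Coverage = P(|t(n-2)| < t(.975, n-2) x sqrt(1-R2)). At n=6 and R2=0.25: 2.776 x 0.866 = 2.404, giving 92.6%.

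| n | R2=0 | 0.1 | 0.25 | 0.5 |
|---|---|---|---|---|
| 6 | 95.0% | 94.2% | 92.6% | 87.9% |
| 10 | 95.0% | 94.0% | 91.9% | 85.8% |
| 14 | 95.0% | 93.9% | 91.6% | 85.1% |

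**Primary endpoint, planned MMRM (simulated, Satterthwaite df).** At the same three non-zero R2 values: n=6, 93.6-94.3%, 91.5-92.7% and 86.6-87.4%; n=14, 93.8-94.0%, 91.3-91.7% and 84.7-85.0%. The same model without baseline covers 94.4-95.2% throughout.

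**When R2=0.** The covariate only costs a degree of freedom. At n=6 the t multipliers are 2.776 (4 df) and 2.571 (5 df), a ratio of 1.080. Multiplying by 0.940/0.9515, the ratio of expected estimated SDs on 4 and 5 df, gives 1.067: the planned CI is about 7% wider than a one-sample t. Average widths are equal at R2 = 1 - 1/1.067^2 = 0.12, or 0.14 from the multipliers alone (1 - 1/1.080^2).

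**Percent against absolute change.** Absolute change = percent change x baseline. If mean percent change is flat in baseline and not zero, mean absolute change is proportional to baseline; if mean absolute change is flat, mean percent change varies with baseline. Unless baselines are nearly equal, both cannot be unrelated to baseline. The exception is a contrived curved relation in which both straight-line slopes vanish.

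If percent response is unrelated to baseline, with mean reduction m, between-patient SD s and baseline CV c, absolute change has R2 = m^2c^2 / (m^2c^2 + s^2(1+c^2)). Simulated coverage with lognormal baselines (ANCOVA against one-sample t):

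| Assumed m, s, c | R2 | With baseline, n=6 / n=14 | Without baseline |
|---|---|---|---|
| 0.30, 0.20, 0.3 | 0.16 | about 93 / 92% | about 95% |
| 0.45, 0.20, 0.4 | 0.41 | about 87 / 86% | about 93-94% |
| 0.59, 0.12, 0.5 | 0.83 | about 63 / 58% | about 92-93% |

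The last row is an extreme corner. Protocol 1.2.2 supplies its mean ("preliminary data showed a mean reduction of 59% in plasma oxalate relative to baseline 28 days after the last dose"). Its SD comes from the range of a different measure, maximal reduction (57-94%; 37/3.08 = 12 points if n=10). Both are from patients with preserved renal function.

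Letting the response run from constant-absolute to proportional (mean 30% or 59%, SD 12 or 20 points, CV 0.3-0.5), the worse of the two ANCOVA CIs covers 62.7-94.3% at n=6 and 58.1-94.2% at n=14.

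**Illustration, assumed values near that corner.** Baselines 30, 40, 55, 70, 90, 120 umol/L; percent changes -47, -71, -55, -65, -69, -47 (mean -59, R2 0.015). Absolute change has R2 0.82.
- LS mean and raw mean: both -39.46.
- With baseline: SE 3.53, CI -49.3 to -29.7.
- Without baseline: SE 7.50, CI -58.7 to -20.2.
- Adding the missing term to the adjusted variance: 3.53^2 + 0.498^2 x 1117.5/6 = 12.5 + 46.2 = 58.7, so SE 7.66, close to the unadjusted value.

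**The case against.** **It is a choice of target.** The CI is valid for the mean at the sample's average baseline, and a feasibility sample with age targets and a 20 umol/L entry floor is not a random draw from a population. The first part is true, but the SAP does not state that target, and its null concerns the mean of the outcome without conditioning.

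**No shortfall is shown for the primary endpoint.** A reader might infer that the primary CI is too narrow whatever the data and whatever df method is used. The documents do not support that. R2 is not given; at R2=0 coverage is exact, and at 0.1 the loss is about one point. At n=6 and R2=0.1, the simulated MMRM with n-2 df covered 95-97%. The problem is material from about R2=0.25. And if percent response is unrelated to baseline, the primary CI is sound and absolute change is the one affected.

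**The largest figures rest on assumptions.** This stands. The 58-63% row should not be read as the expected coverage.

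**Baseline may help with missing data.** In one assumed pattern (about 26% of patients censored after Month 3, more often at high baseline), dropping it moved the estimate by under 1 point. Coverage was 94.1-96.0% without it and 86.1-95.7% with it. Other patterns were not tested.

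**Raw spread is reported anyway.** Descriptive statistics are planned at each visit, but they do not give an interval for the Month 3-6 average and do not replace the model CI.

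**Conclusion.** The point holds in conditional form. SAP 7.1 (both cohorts, fallback included) and 7.3.2 report a CI that suits the mean at the sample's average baseline while the stated null concerns the unconditional mean. The SE is short by sqrt(1-R2) under complete data. How much this affects the primary endpoint cannot be read from the documents: the effect is nil to trivial up to R2 of about 0.1 and material from about 0.25.

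The structural result needs no outside figure. With unequal baselines, percent and absolute change in plasma oxalate cannot both be unrelated to baseline, so in general at least one of the two planned CIs is below nominal. Only the size of that shortfall depends on assumptions, and it runs from trivial to large.

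A reader might go on to infer that a conclusion about efficacy would change. The documents do not support that: Protocol 7.2 calls the analyses primarily descriptive, no success threshold depends on these intervals, and with a mean reduction far from zero the p-value conclusion is unlikely to move. The harm is overstated precision. It is worth correcting because it concerns the reported error bars and costs little to put right.

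**What to change.** For percent and absolute change in plasma oxalate (SAP 7.1, both cohorts, and 7.3.2), do one of the following:
- Take the main LS mean, SE, CI and, in 7.1, p-value from the model without the baseline covariate. The fallback becomes a one-sample t interval on each patient's Month 3-6 average.
- Keep the covariate and add slope^2 x var(baseline)/n to the LS-mean variance.

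Under the first option, keep the baseline-adjusted fit as supportive. Wherever the CI from the adjusted model is shown without the added term, label it as the mean at the sample's average baseline. State the df method, since none is named. Apply the same rule to the urinary endpoints in 7.3.2 for consistency; no size is claimed for them.

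Cost: SAP wording only. At n=6 the unadjusted CI is wider on average once R2 exceeds about 0.12-0.14 and narrower below that. In the MMRM simulations the primary CI was 9-16% wider at R2=0.25 and 35-42% wider at R2=0.5. For absolute change the unadjusted MMRM interval still covers only about 89-94%, because the outcome is skewed; the change removes the covariate's contribution, not that one.
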